#### Pseudocode for Missingness model to estimate fitted probabilities and IPW weights:

Define complete as 1 for complete and 0 for missing and trt=1 for Placebo and 2 for IV bacteriophage.

```

proc logistic data = dat;
  model complete (event='1') = [trt];
  output out = out1 p = probs xbeta = logit;
run;
proc transpose data=out1 out=out2; by patid id trt; var probs; run;
data out2;
  set out2;
  wts=1/(probs_IVB * probs_pbo);
run;

```

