## 6.5. Missing Data

While all efforts will be made to minimize missing data, some missing data is expected. Whenever possible, subjects terminating from the study early will be given an early termination (ET) visit during which the available components of DOOR and related measures can be recorded. A sensitivity analysis of DOOR will be performed using inverse probability weighting (IPW) to reduce the bias in DOOR outcome caused by missing data, assuming a missing at random (MAR) model (see [Section 8.1.3.1](#)). No other endpoints will be analyzed using techniques for missing data.

The effect that any missing data might have on results will be assessed via the inclusion of the IPW sensitivity analysis.

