## 8. MICROBIOLOGICAL ACTIVITY AND BENEFIT TO RISK PROFILE EVALUATION

All variables in the microbiological activity and benefit to risk profile analyses will be listed by subject. Data will be summarized by treatment group. Continuous variables will be summarized with the number of observations, mean, median, SD, quartiles, minimum, and maximum. Categorical variables will be summarized by number and percent in each category. All microbiological activity and benefit to risk profile analyses will be performed using the ITT population.

This study does not include formal hypothesis testing for any of the primary endpoints, and instead relies on CIs for conclusions of treatment effects.

All microbiological activity and benefit to risk profile tables and figures will compare all subjects receiving placebo to all subjects receiving the selected dose of IV bacteriophage chosen from the interim analysis.

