### 8.1.3. Benefit to Risk Profile Analysis Using DOOR

Each subject will have a composite DOOR rank assigned to them based on the presence or absence of SAEs related to study product and the reduction in  $\log_{10} P. aeruginosa$  CFU/mL. DOOR rank will be determined according to the definition in Section 3.3.1.

DOOR probability, which is defined by:

$$DOOR\ probability = Pr[DOOR_2 > DOOR_1] + \frac{1}{2} Pr[DOOR_2 = DOOR_1],$$

will be estimated using the Wilcoxon-Mann-Whitney statistic, correcting for ties and divided by the product of the placebo and IV bacteriophage group sample sizes, where

- DOOR2 and DOOR1 are the DOOR for IV bacteriophage and placebo arms, respectively
- Pr[DOOR2 > DOOR1] is the probability of a DOOR from IV bacteriophage dose being more desirable than a DOOR from placebo, and
- Pr[DOOR2 = DOOR1] is the probability that the DOOR outcomes in IV bacteriophage and placebo are the same.

The corresponding two-sided 95% CI will be calculated using the method described in Halperin et al. [2] for the incorporation of IPW described in Section 8.1.3.1. Note that all CIs are two-sided.

The 95% CI by Halperin et al. [2] will be calculated in the following manner:

- $n_1$ : number of subjects in ITT population randomized to placebo
- $n_2$ : number of subjects in ITT population randomized to IV bacteriophage
- $W$ : Wilcoxon-Mann-Whitney statistic for ordinal outcomes, corrected for ties
- $\zeta$ : DOOR probability
- $\hat{\zeta}$ : An unbiased estimator of  $\zeta$ ,  $\hat{\zeta} = W/(n_1 n_2)$
- $V$ : The variance of the DOOR probability. Correcting for ties, the formula for the variance of the DOOR Probability, as described in Halperin et al. [2], is:

$$\hat{V} = Var(\zeta) = \frac{1}{n_1 n_2} [n_1 + n_2 + 1 - (n_1 + n_2 - 2)\theta] \zeta (1 - \zeta)$$

where

$$\theta = \frac{[(n_1 + n_2 - 2)\zeta - (n_2 - 1)A - (n_1 - 1)B]}{(n_1 + n_2 - 2)\zeta(1 - \zeta)}$$

To obtain an estimator  $\hat{\theta}$  of  $\theta$ , the following formulas will be used for A and B, respectively:

$$\hat{A} = \hat{A}_1 - \frac{1}{n_2 - 1} \sum_{i=1}^{D-1} p_{1i} \left[ q_{2i} \sum_{j=i+1}^D p_{2j} - \left( \sum_{j=i+1}^D p_{2j} \right)^2 \right] - \frac{1}{4(n_2 - 1)} \sum_{i=1}^D p_{1i} p_{2i} q_{2i}$$

where

$$\hat{A}_1 = \sum_{i=1}^{D-1} p_{1i} \left[ \sum_{j=i+1}^D p_{2j} + \frac{p_{2i}}{2} \right]^2 + \frac{p_{1D} p_{2D}^2}{4}$$

and

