$$\hat{B} = \hat{B}_1 - \frac{1}{n_1 - 1} \sum_{j=2}^D p_{2j} \left[ q_{1j} \sum_{i=1}^{j-1} p_{1i} - \left( \sum_{i=1}^{j-1} p_{1i} \right)^2 \right] - \frac{1}{4(n_1 - 1)} \sum_{j=1}^D p_{2i} p_{1i} q_{1i}$$

where

$$\hat{B}_1 = \sum_{j=2}^D p_{2j} \left[ \sum_{i=1}^{j-1} p_{1i} + \frac{p_{1j}}{2} \right]^2 + \frac{p_{11}^2 p_{21}}{4}$$

In the equations for A and B above, D is the number of DOOR outcome ranks in the dataset;  $p_{1i}$ , for  $i = 1, 2, \dots, D$ , represents the proportion of subjects randomized to placebo with the  $i^{\text{th}}$  rank category of DOOR;  $p_{2j}$ , for  $i = 1, 2, \dots, D$ , represents the proportion of subjects randomized to IV Bacteriophage with the  $j^{\text{th}}$  value of DOOR; and  $q = 1 - p$  in general.

Additionally, the equation for an unbiased estimate of  $\zeta(1 - \zeta)$  is given by:

$$\frac{(n_1 n_2 - n_1 - n_2 + 2)\hat{\zeta} - n_1 n_2 \hat{\zeta}^2}{(n_1 - 1)(n_2 - 1)} + \frac{\hat{A}}{n_1 - 1} + \frac{\hat{B}}{n_2 - 1}$$

After substituting the values of A, B and  $\zeta(1 - \zeta)$  in the equation  $\theta$  to obtain an estimate  $\hat{\theta}$  of  $\theta$ ,  $\theta$  is defined as follows: If  $\hat{\theta} < 0$  then  $\theta = 0$ , if  $\hat{\theta} > 1$  then  $\theta = 1$ , otherwise  $\hat{\theta} = \theta$ .

We now compute the pivotal quantity  $Z_H^2 = (\hat{\zeta} - \zeta)^2 / \hat{V}$ .

$$\gamma = (n_1 + n_2 - 1) - (n_1 + n_2 - 2)\hat{\theta}$$

The CI is obtained as the solution set in  $\zeta$  of the quadratic inequality:

$$n_1 n_2 \frac{(\hat{\zeta} - \zeta)^2}{\gamma \zeta (1 - \zeta)} \leq \chi^2(1, 1 - \alpha)$$

Let,  $C = \gamma \chi^2(1, 1 - \alpha) / (n_1 n_2)$ . The CI is given as:

$$\frac{C + 2\hat{\zeta} \pm [C^2 + 4C\hat{\zeta}(1 - \hat{\zeta})]^{1/2}}{2(C + 1)}$$

The superiority of IV bacteriophage vs placebo is concluded if the lower bound of the 95% CI for the DOOR probability is larger than 50%.

Due to the presence of missing data, IPW will be used to handle missing data. For the sensitivity analysis of DOOR, IPW method will be used (see Section 8.1.3.1).

The DOOR will be analyzed as follows:

- DOOR probability with corresponding 95% CI calculated using the method described in Halperin et al. [2] calculated using the greatest reduction in *P. aeruginosa* CFU/mL by Day 8 (Table 26).
- DOOR categories distribution by treatment group through Day 8 + 3 (Table 28).

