#### 8.1.3.1. Intention-to-Treat (ITT) Analysis of DOOR using Inverse Probability Weighting

Intention-to-treat analysis requires that all randomized subjects be included in the analysis. However, missing data is prone to happen in clinical trials due to missing scheduled visits or loss to follow-up for example. In this case, analysis that is only based on complete data may be biased if the excluded subjects are systematically different from those included. IPW is one approach commonly used to reduce this bias under a MAR assumption. This is achieved by weighting complete cases with the inverse of their probability of being a complete case. While subjects missing the DOOR are excluded from the analysis per se, they may still inform the fitting of the logistic regression model used to provide predictions of the probability of completeness which are used to calculate the weights.

Specifically, let  $Y_i$  represent the outcome of interest (DOOR),  $X_i$  represent the covariates of interest,  $Z_i$  represent any other variables measured in the data but not used in the analysis model. For the IPW approach, we first define the missingness model to estimate the weights ( $w_i$ ) using a logistic regression model with outcome  $L$  and covariates taken from set  $(X, Z)$  where  $L_i$  is defined as 1 if DOOR data is complete (not missing) and 0 otherwise. Through this model, we obtain the fitted probabilities of each subject being complete, denoted as  $\pi_i$ .

The DOOR probability can then be calculated using DOOR at Day 8 as the outcome following the algorithm below:

1. Name DOOR from the group that received placebo “sample 1” and the DOOR score ranks from the group that received IV bacteriophage “sample 2”. Rename weights from sample 1 as  $w_{1i}$  and weights from sample 2 as  $w_{2i}$ .
2. Take the first observation in sample 2. If an observation in sample 2 has a smaller DOOR score rank than an observation in sample 1, then that observation in sample 2 gets an indicator of value of 1. Otherwise, if the observation in sample 2 is equal to the observation in sample 1, the observation in sample 2 gets an indicator value of  $\frac{1}{2}$ .
3. Let  $\pi_{1i}$  be the fitted probability of being complete for each observation in sample 1 and  $\pi_{2i}$  be the fitted probability for being complete for each observation in sample 2 obtained from the logistic regression model with an indicator for having non-missing DOOR score rank as the outcome.

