4. For each pair in step 2, create the weight  $w_j$  as the inverse of the probability of both values in the pair being non-missing, i.e.,  $w_j = 1 / (\pi_{1i} \times \pi_{2i})$  with  $j$  being the index for observations in sample 2
5. For each pair in step 2, create the weighted indicator value as  $w\_ind_j = w_j \times indicator_j$
6. Repeat step 2 through 5 for all observations in sample 2.
7. The DOOR probability can then be obtained by  $DOOR\_prob\_IPW = \text{weighted average of all the indicator values in step 5}$ , i.e.;  $DOOR\_prob\_IPW = \frac{\sum_j w\_ind_j}{\sum w_j}$ ,

The DOOR probability (i.e.,  $\text{Pr}(\text{more desirable DOOR in IV bacteriophage}) + 0.5 \text{ Pr}(\text{Equal DOOR})$ ) using IPW is given by the value in  $DOOR\_prob\_IPW$ .

To estimate the 95% CIs for the DOOR probability, the approach discussed in Halperin et al. [2] after incorporating IPW weights is utilized. The superiority of IV bacteriophage vs placebo is concluded if the lower bound of the 95% CI for the DOOR probability is larger than 50%.

IPW will be used to handle missing data for the primary analysis of the DOOR endpoint. Percentage of subjects with missing DOOR data will be presented by time point and treatment group in [Table 25](#).

A tipping point analysis will be performed to estimate the impact of missing data on the primary analysis of the DOOR ([Table 27](#)).

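### If coded as the SAP writes it, inverse probability weighting leaves the DOOR point estimate unchanged, and the addendum drops the only analysis that imputes ranks for DOOR missing for reasons other than undetectable counts

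*SAP*

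**What the plan says.** SAP 8.1.3.1 gives the reason for weighting: "analysis that is only based on complete data may be biased if the excluded subjects are systematically different from those included". A logistic model for having a DOOR supplies the fitted probabilities. Each placebo–phage pair is weighted by the inverse product of its two probabilities, and the DOOR probability is the weighted sum of indicators divided by the sum of weights. Covariates come from a generic set (X, Z), with no variable named. The pseudocode that follows has one model line, "model complete (event='1') = [trt", with the arm variable in square brackets.

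SAP 6.5 gives this analysis its purpose: "The effect that any missing data might have on results will be assessed via the inclusion of the IPW sensitivity analysis". Its role is stated two ways. SAP 8.1.3.1 says "IPW will be used to handle missing data for the primary analysis of the DOOR endpoint", while SAP 8.1.3 says "For the sensitivity analysis of DOOR, IPW method will be used", and 6.5 also calls it a sensitivity analysis. Table 26 and addendum Tables 14 and 15 print DOOR with and without IPW side by side.

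SAP 8.1.3 defines n1 as the "number of subjects in ITT population randomized to placebo" and n2 likewise for phage, and estimates DOOR as W/(n1 n2). Section 8.1.3.1 says "While subjects missing the DOOR are excluded from the analysis per se".

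SAP v1.0 had one grid that imputed ranks for missing DOOR, Table 27. Addendum 2.1 replaces it with Table 30, which varies the percentage of undetectable counts set to 10^4 CFU/mL. Protocol 10.5.8 promises sensitivity analyses suited to the missing-data pattern that is seen, but specifies none.

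**The concern.** A logistic model on a two-level arm variable is saturated, so it gives one fitted probability per arm. Under the SAP's normalised estimator that probability has no influence on the point estimate. A reader of Tables 14 and 15 would see two matching estimates and could take the match as evidence of robustness, although it follows from the algebra.

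Once Table 27 is gone, nothing pre-specified asks what happens if subjects whose DOOR is missing through missed visits, withdrawal or absent sputum did systematically better or worse than those observed.

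The trial does no formal testing, but SAP 8 says that it "instead relies on CIs for conclusions of treatment effects", and 8.1.3 concludes superiority when the lower limit for DOOR exceeds 50%. With 20 to 25 subjects per arm, one or two outcomes can decide which side of that line the limit falls on.

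**Working it through.** **Design figure.** The only numeric DOOR figure in the plan is 51% to 89% for a true value of 70% with 20 per arm (Protocol 10.2). Using the null Wilcoxon variance without ties, 0.70 ± 1.96 × √((20+20+1)/(12×20×20)) = 0.70 ± 0.181, or 51.9% to 88.1%. That is within one point of the stated limits, and nothing below depends on it.

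**Point estimate under the arm-only model.** Let π1 and π2 be the fitted completeness probabilities for placebo and phage. Each is constant within its arm, so every pair has weight w = 1/(π1π2). Then Σ(w × indicator)/Σw = w Σ(indicator)/(w × number of pairs), which is the unweighted mean. Coding the SAP algorithm on simulated datasets of 18 to 25 per arm gave a largest difference of 4.4×10⁻¹⁶, which is rounding error. Adding one baseline covariate related to both outcome and missingness (an assumption) moved single-dataset estimates by up to 0.24. The equality therefore comes from the arm-only model and is not a general property of IPW.

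**Intervals.** The SAP does not spell out how the weights enter the Halperin interval. For phage ranks 1/2/3 of 4/6/9 against placebo 1/3/15, the lower limit is 0.505 with observed n (19 per arm) and 0.509 with randomized n (20 per arm).

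**What a rank-imputation grid would show.** The counts are assumed, with 20 randomized and 19 observed per arm, no related SAE, and the Halperin formulas of SAP 8.1.3 with γ as printed there.

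| Observed, phage vs placebo | Complete cases | Missing phage rank 3, missing placebo rank 2 |
|---|---|---|
| 4/6/9 vs 1/3/15 | 240.5/361 = 0.666 (0.505–0.796) | 255/400 = 0.638 (0.480–0.770) |
| 5/6/8 vs 1/3/15 | 251.5/361 = 0.697 (0.534–0.822) | 267/400 = 0.668 (0.508–0.796) |

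The first conclusion reverses and the second is kept. If both missing subjects in the first row are rank 3, the lower limit is 0.503 and the conclusion is kept.

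**How often.** This is an exact enumeration over three assumed pairs of rank 1/2/3 distributions, phage vs placebo in percent: 40/27/33 vs 15/20/65, 26/32/42 vs 5/15/80, and 20/40/40 vs 2/14/84. The true DOOR probabilities are 0.68, 0.70 and 0.73. The last two columns give the share of complete-case superiority conclusions that reverse.

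| Randomized per arm | Missing per arm | Phage rank 3, placebo rank 2 | Both rank 3 |
|---|---|---|---|
| 20 | 1 | 12–19% | 1–3% |
| 20 | 2 | 32–40% | 2–7% |
| 25 | 1 | 6–13% | 0–2% |
| 25 | 2 | 18–29% | 1–4% |

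With 20 per arm and one missing, 55–84% of trials conclude superiority on complete cases.

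**Denominators.** With 19 of 20 observed per arm, an unweighted W over randomized n gives 240.5/400 = 0.601 instead of 0.666. A weighted W is not affected: the weights over the 361 observed pairs sum to 361/0.9025 = 400, so dividing by 400 returns 0.666.

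**The case against.** The strongest reply is that the bracketed arm term is a placeholder. The SAP uses square brackets for fill-in fields elsewhere, the block is labelled pseudocode, and the prose draws covariates from anything measured. That is a fair reading, and it means that the final analysis need not be inert. It does not close the gap: with no covariate named, either the model is arm-only or its predictors are chosen later without pre-specification.

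Second, DOOR uses the greatest reduction by Day 8, so it is lost only if baseline or all four post-dose samples (Day 1 post-infusion, Days 2, 5 and 8) are missing. The only missing DOOR reported, 5 of 32 interim subjects, came from undetectable counts. Those are substituted in Table 14 and varied in Table 30. This stands: one or two missing per arm for other reasons is an assumption, and the higher reversal rates also assume outcomes that run in opposite directions by arm.

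Third, Protocol 10.5.8 already commits to missing-data sensitivity analyses. It does, but it leaves the method and the scenarios open.

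A reader might infer two stronger things. One is that the columns with and without IPW are the same analysis throughout. Only the point estimates are shown to be equal; the intervals may differ. The other is that the randomized-n definition shrinks the IPW estimate. It does not: 8.1.3.1 divides by the sum of weights, so the 0.601 figure concerns the unweighted column only.

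**Conclusion.** The point holds in conditional form. If the completeness model is coded as written, the IPW point estimate equals the complete-case one for any missingness rates, and it cannot serve the purpose given in SAP 6.5 and 8.1.3.1. With Table 27 replaced, no departure from missing at random is pre-specified for DOOR missing for reasons other than undetectable counts.

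The size in primary Table 14 is unknown and may be nil, because the documents report no such missingness. It would be tempting to say that the primary DOOR result is biased or fragile; the documents do not support that. Reversal needs missing subjects, a result near the threshold and unfavourable missing ranks. The one place with documented missing DOOR is Table 15, where undetectable counts are treated as missing (5 of 32 at the interim, with no split by arm). There too an arm-only IPW column adds nothing to the point estimate. The severity is minor to should-fix.

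**What to change.** 1. Keep a Table 27-type rank-imputation grid beside Table 30 for DOOR missing for reasons other than undetectable counts. Limit it to ranks 1 to 3 where follow-up to Day 8 shows no related SAE.
2. State in Tables 14 and 15 that the arm-only IPW point estimate equals complete-case and is not evidence of robustness. Alternatively, pre-specify a predictor observed for all randomized subjects. Baseline log10 CFU does not qualify in Table 15: 3 of the 5 affected interim subjects had undetectable baselines, which are missing there.
3. For the unweighted estimate and its interval, define n1 and n2 as subjects with non-missing DOOR. For the weighted estimate, divide by the sum of weights as 8.1.3.1 does; dividing a weighted W by observed pairs would inflate 0.666 to 0.666 × 400/361 = 0.738. Spell out how the weights enter the Halperin interval, and say once whether IPW is primary or sensitivity.

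The cost is SAP wording, one footnote and one table shell that is already drafted. It needs no new data and no change to conduct. A predictor, if chosen, would add some variance to the weights, and with one or two non-completers per arm it could hardly be estimated, so the footnote is the more practical option.

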## 8.2. Exploratory Analyses

### 8.2.1. Change in Lung Function Through Day $30 \pm 7$

Lung function will be measured using FEV1 from spirometry measurements collected at Days 1(Baseline), 2, 5, and 30.

The absolute change in lung function measured by FEV1 will be summarized by number of subjects, mean, SD, median, quartiles, minimum, and maximum in [Table 34](#). The percent change in predicted FEV1 from baseline to Days 2, 5, and 30 will be presented by treatment group in [Table 35](#). Predicted FEV1 will be calculated using the Global Lung Function Initiative (GLI) global standards. The baseline and post-baseline measures will be log-transformed before calculation of the percent change, then back-transformed before calculating the mean.

### 8.2.2. Characterization of Geographically Diverse *P. aeruginosa* Isolates Susceptibility to Bacteriophages

The changes in  $\log_{10} P. aeruginosa$  colony counts through Day  $30 \pm 7$  will be summarized by morphology and treatment group in [Table 36](#). Changes will be summarized by number of subjects, mean, SD, median, quartiles, minimum, and maximum.

The proportion of *P. aeruginosa* isolates susceptible to each dose of bacteriophage will be presented by dose in [Table 37](#). The 95% CI for the proportion of susceptible isolates in each treatment group will be calculated using the Wilson method and the 95% CI for the difference between IV bacteriophage and placebo will be calculated using the Miettinen–Nurminen method. Susceptibility testing results will be presented in [Listing 13](#). Phage quantitative polymerase chain reaction (qPCR) results will be presented in [Listing 14](#).

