#### **3.2.3. Exploratory**

- Population mean PK parameter estimates and the magnitude of the associated inter-individual variability for IV bacteriophage therapy in serum and sputum.
- Individual post hoc PK parameter estimates and calculated exposure measures in serum for IV bacteriophage therapy.

- Individual post hoc PK parameter estimates and calculated exposure measures in sputum for IV bacteriophage therapy.
- Changes in the forced expiratory volume in 1 second (FEV1) from the administration of IV bacteriophages through Day  $30 \pm 7$  days.
- Changes in  $\log_{10} P. aeruginosa$  colony counts of each morphology in quantitative sputum cultures from administration of IV bacteriophages through Day  $30 \pm 7$ .
- Proportion of *P. aeruginosa* isolates susceptible to individual bacteriophages and the bacteriophage cocktail.
- Change from baseline through Day  $30 \pm 7$  follow-up visit of QoL as measured with the Cystic Fibrosis Questionnaire-Revised (CFQ-R) and the Cystic Fibrosis Respiratory Symptom Diary (CFRSD).

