## 4.6. Exploratory Endpoint Variables

There will be four exploratory objectives: (1) characterize the serum and sputum PK profiles of a single dose of IV bacteriophage therapy in clinically stable CF subjects with *P. aeruginosa* in expectorated sputum, (2) change in lung function from the administration of a single dose of IV bacteriophage therapy through Day  $30 \pm 7$ , (3) characterize geographically diverse *P. aeruginosa* isolates susceptibility to bacteriophages, and (4) describe subjects' QoL before and after receiving bacteriophages. The SAP for the first exploratory objective, related to serum and sputum PK, will be provided in a separate document.

Change in lung function will be measured using FEV1. Spirometry will be performed at screening, baseline, and at follow-up visits occurring on Days 2, 5, 12, and 30.

Phage susceptibility testing (PST) will occur using a plaque assay and the liquid assay. These assays describe the proportion of *P. aeruginosa* isolates that are susceptible to each phage and to the phage cocktail. Both the plaque assay and liquid assay will be evaluated every time sputum is obtained (see schedule of study

procedures in [Table 1](#)). An isolate will be considered susceptible to phage if both the plaque assay and the liquid assay indicate susceptibility.

The CFQ-R (<https://cfqr-app.netlify.app/#/questionnaire>) is a self-administered QoL questionnaire designed to measure the impact that CF has on overall health, daily life, and perceived well-being and symptoms. The CFQ-R contains 50 items and will be administered at in-person and virtual study visits for Stage 2 subjects. The CFRSD (<https://depts.washington.edu/seaqol/CFRSD-CRISS>) is a subject reported outcome measure that is used to evaluate the effect of treatment on respiratory infection symptom severity in patients with CF and chronic respiratory infection. Quality of Life will be measured using the CFQ-R and the CFRSD. The CFQ-R will be administered at baseline and at the final follow-up visit (Day  $30 \pm 7$ ). The CFRSD will be administered at baseline and at follow-up visits occurring on Day 2, 5, 8, and 30.

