Maximum	Selected Dose (N=X)	x	xx.x	xx.x	xx	xx, xx	xx, xx	xx, xx	xx.x	xx.x	xx	xx, xx	xx, xx	x.xx, x.xx	
	Placebo (N=X)	x	xx.x	xx.x	xx	xx, xx	xx, xx	xx, xx	xx.x	xx.x	xx	xx, xx	xx, xx	x.xx, x.xx	
[Repeat for all morphologies]															

Notes: N=Number of subjects in the ITT population in Stage 2a and 2b.

n=Number of subjects in the ITT population in Stage 2a and 2b with non-missing colony counts at the time point of interest. For the change from baseline, n represents the number of subjects in the ITT population with non-missing values at baseline and at the time point being assessed.

SD=Standard Deviation

Baseline is defined as the last measurement taken prior to dosing on Study Day 1.

aQ1 and Q3 represent the 25th and 75th percentiles, respectivelyb95%CI is calculated from a t-distribution.

**Table 37: Proportion of *P. aeruginosa* Isolates Susceptible to Individual Bacteriophages – ITT Population, Stage 2a and 2b**

[Implementation note: ‘Selected Dose’ will be replaced with the dose chosen by the interim analysis. If multiple timepoints are collected, then this table will be stratified by timepoint with an additional ‘All Timepoints’ category.]

P. aeruginosa Isolate	Selected IV Bacteriophage Dose				Placebo				Difference 95% CI b
	N	n	%	95% CI a	N	n	%	95% CI a	
[Bacteriophage 1]									
[Isolate 1]	x	x	x	(x.x, x.x)	x	x	x	(x.x, x.x)	xx (x.x, x.x)
[Isolate 2]	x	x	x	(x.x, x.x)	x	x	x	(x.x, x.x)	xx (x.x, x.x)
[Isolate 3]	x	x	x	(x.x, x.x)	x	x	x	(x.x, x.x)	xx (x.x, x.x)
[Isolate 4]	x	x	x	(x.x, x.x)	x	x	x	(x.x, x.x)	xx (x.x, x.x)
[Repeat for each bacteriophage]									

Notes: *P. aeruginosa* isolate will be identified by individual morphotype ID.

N=Number of subjects in the ITT population in Stage 2a and 2b with non-missing values for isolate susceptibility.

n=Number of subjects with isolates susceptible to the corresponding bacteriophage.

a95% CI for proportions calculated using the Wilson method.

b95% CI for the difference in proportions, IV bacteriophage relative to placebo, calculated using the Miettinen–Nurminen method.

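### SAP Section 8.2.2 and Table 37 do not deliver the stated susceptibility endpoint: no row pools isolates within a phage, and the cocktail is not summarised at all

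*SAP*

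**What the plan says.** The endpoint is stated consistently. Protocol Section 3.3.3 and SAP Section 3.2.3 both give the proportion of *P. aeruginosa* "isolates susceptible to individual bacteriophages and the bacteriophage cocktail". SAP Section 4.6 repeats it as the proportion of "isolates that are susceptible to each phage and to the phage cocktail", and adds a rule at isolate level: "An isolate will be considered susceptible to phage if both the plaque assay and the liquid assay indicate susceptibility". With four phages in the product, that is five proportions, each with the isolate as the unit.

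The analysis text in SAP Section 8.2.2 departs from this. It says that the proportion of "isolates susceptible to each dose of bacteriophage will be presented by dose in" Table 37, and names neither the individual phages nor the cocktail. The next sentence returns to isolates: "The 95% CI for the proportion of susceptible isolates in each treatment group will be calculated using the Wilson method". A Miettinen–Nurminen interval is planned for the difference between arms.

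The Table 37 shell differs from both. Its title refers to individual bacteriophages. Under each phage there is one row per isolate, and the notes say that each "isolate will be identified by individual morphotype ID". The denominator is given as "N=Number of subjects in the ITT population in Stage 2a and 2b with non-missing values for isolate susceptibility", and the numerator is also a count of subjects. The block is repeated for each phage and then ends. If several time points are available, the table is split by time point and gains a category for all time points together.

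**The concern.** The endpoint, the analysis text and the table shell describe three different quantities: by phage and cocktail, by dose, and by phage and morphotype ID. A programmer following the shell would produce a table from which a reader could not read off what share of isolates any phage covers, and which says nothing about the cocktail, the product actually infused.

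The matter is worth settling because describing isolate susceptibility is one of the four exploratory objectives, and because subjects are not screened for susceptibility before dosing (Protocol Section 3.1). Phage coverage in the enrolled population will be known only from these assays.

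**Working it through.** The documents give no expected proportion, sample size or precision for this endpoint, so there is no stated figure to reproduce. The check sets the specifications side by side and then uses small illustrations.

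**1. Side by side**

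| Source | Susceptible to what | Unit counted | Row for all isolates | Cocktail |
|---|---|---|---|---|
| Protocol 3.3.3, SAP 3.2.3, SAP 4.6 | each phage and the cocktail | isolate | is the endpoint | yes |
| SAP 8.2.2 | each dose | isolate (Wilson sentence) | not specified | not named |
| SAP Table 37 | each phage | subject | none | none |

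The only pooled category in Table 37 is over time, not over isolates. Listing 13 does not fill the gap. Each subject and time point has one plaque result and one liquid result, with no isolate identifier and no result per phage or for the cocktail. The later SAP document on undetectable colony counts lists no replacement for Table 37.

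**2. What a row contains, by meaning of morphotype ID**

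- *Unique to one subject.* N = 1 in one arm and 0 in the other. The Wilson 95% interval for 1/1 has lower limit 1/(1 + z²) = 1/(1 + 3.84) = 20.7% and upper limit 100%. For 0/1 it is 0% to 79.3%. The difference between arms cannot be computed.
- *A running number within subject.* Assume 20 subjects: 10 have one isolate, which is susceptible, and 10 have three isolates, of which only the first listed is susceptible. Table 37 prints 20/20, 0/10 and 0/10 in three rows. The isolate proportion, 20/40, is not printed.
- *A class shared across subjects.* If each subject has at most one isolate per class and visit, n/N is the proportion for that class. The proportion over all isolates is again not printed.

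**3. Why the unit matters**

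In the same assumed data, the isolate proportion is 20/40 = 50% (Wilson 35.2% to 64.8%, ignoring clustering). Counting subjects with any susceptible isolate gives 20/20 = 100% (83.9% to 100%). At the maximum arm size of 25, with 12 subjects having one isolate and 13 having three on the same pattern, the figures are 25/51 = 49.0% (35.9% to 62.3%) and 25/25 = 100% (86.7% to 100%).

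**4. Whether the cocktail can be derived**

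Suppose an isolate counts as susceptible to the cocktail if at least one phage is active. With per-phage proportions p₁ to p₄, the cocktail proportion lies between max(pᵢ) and min(1, Σpᵢ).

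| Each phage | Cocktail range |
|---|---|
| 10% | 10% to 40% |
| 25% | 25% to 100% |
| 40% | 40% to 100% |

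If the cocktail instead has its own assay result, as Section 4.6 suggests, even these bounds need not hold. The four per-phage proportions do not determine the fifth.

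**The case against.** The strongest reply is that this is an inconsistency of wording and layout on a descriptive endpoint. The endpoint itself is stated correctly three times, the Wilson sentence in 8.2.2 puts the interval on isolates, and the Table 37 title names individual bacteriophages. By dose may be loose wording for treatment group. Protocol Section 7.2.2 makes the testing depend on sample availability, and SAP Section 6.8 plans no formal tests. All of this stands. It limits the importance of the point, but it supplies neither the missing rows nor the cocktail result.

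A reader might go further in four ways that the documents do not support.

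- *That every row must compare one subject with none.* This follows only if morphotype IDs are unique to a subject. Table 36 summarises colony counts by morphology across subjects in each arm, which makes sense only if morphologies recur, so a shared-class reading is open. Listing 11, which keeps the ID separate from colony size, color and mucoid phenotype, points somewhat the other way. The SAP leaves it undefined.
- *That no per-phage proportion could be obtained.* Under the running-number or shared-class reading, with one isolate per row, subject and time point, n and N could be added by hand. No such total or interval is planned.
- *That the category for all time points treats repeat isolates as independent.* With subjects as the unit, each might be counted once. The shell does not say, so the category is undefined rather than shown to be wrong.
- *That nothing else reports susceptibility.* Tables 22, 29 and 30 split subjects into susceptible and not susceptible and carry the question of whether susceptibility relates to response. That is a subject-level split, not the proportion of isolates, and nothing makes it depend on the Table 37 layout.

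**Conclusion.** The concern holds as a mismatch between a stated exploratory endpoint and its planned analysis. As written, none of the five proportions is printed for all isolates. For the four phages this is a missing summary that could be repaired by hand under some readings of morphotype ID. For the cocktail it is a full gap, because there is no row, no listing column and no way to derive the result from the per-phage figures. The absence of a pooled row and a cocktail row is plain from the shell and rests on no assumption. The degree of sparseness does rest on one, the meaning of morphotype ID, and the 50% against 100% contrast rests on assumed isolate counts. The primary results do not depend on Table 37. The change is worth making before the analysis because it is small and restores an endpoint that both documents state.

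**What to change.** - **Section 8.2.2:** replace the reference to dose with *to each phage and to the phage cocktail, by treatment group and time point*.
- **Table 37:** add one row per phage pooled over isolates and one row for the cocktail. The numerator is isolates susceptible by both assays and the denominator is isolates tested. State how cocktail susceptibility is determined (its own assay result, or susceptibility to at least one phage). Define morphotype ID if the detailed rows are kept.
- **Interval:** use one that allows for several isolates per subject, since Wilson and Miettinen–Nurminen assume independent units.
- **Time points:** show the pre-dose time point separately. Either drop the category for all time points or state how repeat isolates from one subject are counted.
- **Listing 13:** add columns for isolate, phage and cocktail result.

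The cost is SAP wording, one table shell and one listing. No new samples or assays are needed, because pre-dose sputum is already collected and Section 4.6 already describes testing against each phage and the cocktail.

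The interval will usually be wider than Wilson, by an amount that depends on within-subject correlation ρ, which the documents do not give. For the cluster sizes in the 20-subject illustration, the design effect is 1 + (2.5 − 1)ρ, where 2.5 = (10×1² + 10×3²)/40. It runs from 1 (ρ = 0) to 2.5 (ρ = 1), so 40 isolates carry the information of 40 down to 16. At a proportion of 50% the half-width is (z/2)/√(n + z²), which goes from 0.98/√43.84 = 14.8 points to 0.98/√19.84 = 22.0 points.
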